7. EFFICACY ANALYSES

7.1. Primary Efficacy Analyses

7.1.1. Endpoint / Variables

Proportion of participants with plasma HIV-1 RNA ≥ 50 c/mL as per Food and Drug Administration (FDA) Snapshot algorithm at Week 48 (Intent-to-Treat Exposed [ITT-E] population); see Section 15.9 for additional details.

7.1.2. Summary Measure

Difference in the proportion of participants with HIV-1 RNA ≥ 50 c/mL at Week 48 (defined by the US FDA snapshot algorithm) between each treatment group (Q8W – Q4W).

7.1.3. Population of Interest

The primary efficacy analyses will be based on the Intent-to-Treat Exposed population, unless otherwise specified.

7.1.4. Strategy for Intercurrent (Post-Randomization) Events

As defined by the Snapshot algorithm, HIV-1 RNA ≥ 50 c/mL is determined by the last available HIV-1 RNA measurement while the participant is on treatment within the analysis visit window of interest.

Participants without on-treatment HIV-1 RNA data for the visit of interest and who discontinue treatment for reasons not related to adverse event while having HIV-1 RNA ≥ 50 c/mL at time of discontinuation or who change study treatment not permitted per protocol before the analysis window are classified as having HIV-1 RNA ≥ 50 c/mL.

7.1.5. Statistical Analyses / Methods

Details of the planned displays are provided in Appendix 15: List of Data Displays and will be based on GSK data standards and statistical principles.

Unless otherwise specified, endpoints / variables defined in Section 7.1.1 will be summarised using descriptive statistics, graphically presented (where appropriate) and listed.

7.1.5.1. Statistical Methodology Specification

| Endpoint |
|--|
| 
 Proportion of Participants with plasma HIV-1 RNA ≥ 50 c/mL at Week 48 using the Snapshot algorithm for the ITT-E population. Subjects with 'HIV-1 RNA ≥ 50 c/mL' per Snapshot algorithm include those who had plasma HIV-1 RNA ≥ 50 c/mL at Week 48, who discontinued for lack of efficacy, who discontinued for other reasons while not <50 c/mL, or who changed ART. |

Snapshot Dataset

- Virologic outcome ('HIV-1 RNA <50 c/mL' or 'HIV-1 RNA \geq 50 c/mL') per Snapshot algorithm is determined by the last available on-treatment HIV-1 RNA measurement within the analysis visit window of interest (please refer to analysis window defined in [Table 10](#)). In addition, subjects who discontinue for reasons not related to adverse event with on-treatment HIV-1 RNA result at the time of discontinuation \geq 50 c/mL or who change study treatment not permitted per protocol during maintenance phase before the analysis visit are classified as 'HIV-1 RNA \geq 50 c/mL'.
- Full details of the Snapshot algorithm are provided in [Section 15.9](#).

Model Specification

- The primary efficacy endpoint will be analysed using a stratified analysis with Cochran-Mantel-Haenszel (CMH) weights, adjusting for the rederived randomization strata corresponding to prior exposure to CAB+RPV (0 weeks, 1-24 weeks, >24 weeks)
- The CMH estimate of the adjusted treatment difference will be calculated as a weighted average of strata-specific estimates of the treatment difference calculated within each stratum as follows:
 - If n_k is the number of Q8W treated participants, m_k is the number of Q4W arm treated participants, and $N_k = n_k + m_k$ is the total number of participants in the k th stratum, then the CMH estimate is given by

$$\hat{d}_{cmh} = \frac{\sum W_k \hat{d}_k}{\sum W_k}$$

where

$$W_k = \frac{n_k m_k}{N_k}$$

are CMH weights and \hat{d}_k are estimates of the differences in proportions between the two treatment arms, $f_{Q8W} - f_{Q4W}$, for the k th stratum.

- The corresponding two-sided 95% CI will be calculated as

$$\hat{d}_{cmh} \pm 1.96 \times \sqrt{\text{var}(\hat{d}_{cmh})}$$

where the variance estimator [[Sato, 1989](#)] is consistent in both sparse data and large strata and is given below:

$$\text{var}(\hat{d}_{cmh}) = \frac{\hat{d}_{cmh}(\sum P_k) + \sum Q_k}{(\sum n_k m_k / N_k)^2} = \frac{\hat{d}_{cmh}(\sum P_k) + \sum Q_k}{(\sum W_k)^2}$$

where

$$P_k = \frac{n_k^2 y_k - m_k^2 x_k + n_k m_k (m_k - n_k) / 2}{N_k^2}$$

$$Q_k = \frac{x_k (m_k - y_k) / N_k + y_k (n_k - x_k) / N_k}{2}$$

with x_k and y_k corresponding to the number of participants with Plasma HIV-1 RNA ≥ 50 c/mL at Week 48 per FDA Snapshot for Q8W and Q4W, respectively, for the k th stratum.

Model Results Presentation

- Adjusted CMH estimate of the difference in the proportion of subjects with Plasma HIV-1 ≥ 50 c/mL between each treatment group (Q8W – Q4W) and corresponding 95% confidence interval.
- Non-inferiority will be concluded if the upper bound of the two-sided 95% confidence interval for the CMH adjusted treatment difference (Q8W – Q4W) is less than 4%.
- If this analysis shows non-inferiority, then a superiority hypothesis will be tested at the two-sided 5% level of significance. Superiority favoring Q8W will be declared if the upper bound of the confidence interval is below 0% for the ITT-E population analysis. If superiority is declared, the p-value for superiority will also be calculated.

Subgroup Analyses

- Treatment Heterogeneity across rederived randomization strata [prior exposure to CAB+RPV (0 weeks, 1-24 weeks, >24 weeks)]:
 - The weighted least squares chi-squared statistic [Fleiss, 1981] will be used to test for one-way homogeneity across the levels of each categorical variable, with each categorical variable considered separately.
 - Following Lui and Kelly [Lui, 2000] $\frac{1}{2}$ will be added to each cell in any strata for which the stratum-specific rate estimates of either f_{Q8W} or f_{Q4W} are zero or one, and tests will be one-sided.
 - Any heterogeneity found to be statistically significant will be explored and if necessary results will be reported for each level of the categorical variable. Investigation of heterogeneity will be confined to the primary endpoint. Tests of homogeneity will be assessed at the one-sided 10% level of significance.
- Stratum-specific analyses for two groups of participants: (Group 1) those currently receiving Standard of Care antiretroviral therapy at Baseline (i.e. no prior exposure to CAB+RPV), (Group 2) those receiving Q4W CAB LA + RPV LA therapy in the ongoing ATLAS study (i.e. have prior exposure to CAB+RPV). For each stratum (Group 1 and Group 2), the following will be presented:
 - Proportion of subjects with plasma HIV-1 RNA ≥ 50 c/mL at Week 48 by treatment group.
 - Unadjusted difference in proportions between treatment groups and corresponding two-sided 95% CI.
 - Summary of study outcomes (i.e. HIV-1 RNA < 50 c/mL, HIV-1 RNA ≥ 50 c/mL and reason for no data in the window)

For Group 2, a stratum-adjusted analysis will also be provided, with adjustment for prior CAB+RPV exposure (1 to 24 weeks vs. >24 weeks) using Cochran-Mantel Haenszel (CMH) weights, as described in the model specification above for the overall primary analysis.

3. Exploration of Subgroups

- An analysis for subgroups listed in Section 5.4.2 will be performed. This will show the proportion of subjects with plasma HIV-1 RNA ≥ 50 c/mL at the time of analysis (Week 48) based on the Snapshot algorithm and will be presented by treatment group.
- Unadjusted difference in proportions between treatment groups and corresponding two-sided 95% CI will also be presented by subgroups. The confidence interval will be calculated using an unconditional exact method [Chan, 1999] with two inverted one-sided tests based on the score statistic. These results will also be presented graphically.
- Summary of study outcomes (i.e. HIV-1 RNA < 50 c/mL, HIV-1 RNA ≥ 50 c/mL or reason for no data in the window) by subgroup will be produced.

Note: These subgroup analyses will be exploratory and likely underpowered so that interpretation may therefore focus on point estimates as well as the upper bounds of 95% CIs for the treatment differences and response rates. Additionally, multiple comparisons are being made which inflates the risk of false positive findings. Therefore, if consistent findings across the multiple comparisons were observed then these analyses would still be suggestive of a generalizable finding of non-inferiority.

Sensitivity and Supportive Analyses

1. Per-protocol population analysis:

- To assess the impact of important protocol deviations, statistical analysis will be repeated using the Per-protocol population and compared for consistency with the results from the primary ITT-E population analysis.

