2.3. Study Design

Overview of Study Design and Key Features

Main Study:

[figure not shown]

N=1020, randomized 1:1 to each arm and stratified by prior CAB+RPV Exposure

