2.4. Statistical Hypotheses / Statistical Analyses

The study is designed to demonstrate that the antiviral effect of Q8W dosing with CAB LA + RPV LA is non-inferior to Q4W dosing CAB LA + RPV LA in subjects stably suppressed on an oral SOC regimen or Q4W CAB LA + RPV LA regimen prior to randomization. Non-inferiority in the proportion of participants with HIV-1 RNA ≥ 50 c/mL at Week 48 (defined by the US FDA snapshot algorithm) can be concluded if the upper bound of a two-sided 95% confidence interval for the difference between the two treatment arms (Q8W – Q4W) is less than 4%.

If f_{Q8W} is the snapshot failure rate for Q8W CAB LA + RPV LA, and f_{Q4W} is the snapshot failure rate for Q4W CAB LA + RPV LA then the null (H_0) and alternative (H_a) hypotheses can be written as follows:

$$H_0: f_{Q8W} - f_{Q4W} \geq 4\% \text{ vs } H_a: f_{Q8W} - f_{Q4W} < 4\%$$

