5.5. Multiple Comparisons and Multiplicity

5.5.1. Primary Comparison of Interest

The primary analysis will be based on the ITT-E population. The primary comparison will be made at a one-sided 2.5% level of significance. Treatment with Q8W will be declared non-inferior to Q4W if the upper end of a two-sided 95% confidence interval for the difference between the two groups (Q8W – Q4W) in the proportion of participants with HIV-1 RNA ≥ 50 c/mL at Week 48 (defined by the US FDA snapshot algorithm) lies below 4%.

The primary comparison of interest is the comparison between Q8W (CAB LA + RPV LA Q8W) and Q4W (CAB LA + RPV LA Q4W) for the primary endpoint in the ITT-E population. This analysis will be adjusted for by the re-derived randomization strata based on eCRF data.

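### The primary non-inferiority rule is a Wald-type interval whose one-sided error exceeds the stated 2.5%: about 2.9–4.0% if the Q4W failure rate is 0.5–3%, a rate the SAP does not state

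*SAP*

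**What the plan says.** Section 5.5.1 fixes the level: "The primary comparison will be made at a one-sided 2.5% level of significance". Section 2.4 fixes the margin: non-inferiority requires that the upper bound for the "difference between the two treatment arms (Q8W – Q4W) is less than 4" per cent. Section 7.1.5.1 turns this into a rule: "Non-inferiority will be concluded if the upper bound of the two-sided 95% confidence interval" for the CMH-adjusted difference is below the margin. On the interval itself it says: "The corresponding two-sided 95% CI will be calculated as" the CMH estimate ± 1.96 × √variance, with the Sato variance computed from the observed counts in three prior-exposure strata. The SAP supports that variance with one property, that it "is consistent in both sparse data and large strata".

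The only sensitivity analysis listed for the primary endpoint repeats the same method in the Per-Protocol population. For exploratory subgroups the same section uses another interval, unconditional exact and unadjusted, "with two inverted one-sided tests based on the score statistic". Section 5.4.1 carries the CMH approach to Weeks 96 and 152.

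**The concern.** Consistency of a variance estimator is a large-sample property. It does not ensure that a test holds its level when each arm has only a few failures.

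At the edge of the null hypothesis the Q8W failure rate is 4 percentage points above the Q4W rate, and the Q8W count is right-skewed. When that count is low by chance, the difference is underestimated and so is its variance, because the variance comes from the same low count. The symmetric upper limit then falls below 4% more often than intended. A score interval avoids this by evaluating the variance with the difference held at 4%.

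What is at stake is the level of the test that opens the sequence in Section 5.5.2. An excess here favours Q8W and also passes to the key secondary comparisons that are tested only after this one. The Per-Protocol repeat cannot reveal the problem, because it uses the same interval.

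**Working it through.** **Inputs from the SAP.** One-sided level 2.5% (Section 5.5.1); margin 4 points (Section 2.4); rule and variance (Section 7.1.5.1); size from Section 2.3, "N=1020, randomized 1:1 to each arm and stratified by prior CAB+RPV Exposure", so 510 per arm.

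**Inputs assumed.** The SAP gives no Q4W failure rate and no stratum sizes. The rate is varied from 0.1% to 10%. Three stratum splits per arm are tried: 320/70/120, 255/60/195 and 170/170/170.

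**The plan's own figure.** 1 − Φ(1.96) = 0.0250, so the nominal level is reproduced. The sample size cannot be checked, because no rates or power are stated. For orientation, equal 4% rates at 90% power need (1.96 + 1.2816)² × 2 × 0.04 × 0.96 / 0.04² ≈ 504.4, or 505 per arm. A 4% rate is therefore a possible but unstated basis.

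**The rule on one data set.** Take 15 Q8W and 3 Q4W failures, 510 per arm, one stratum.
- W = 510 × 510 / 1020 = 255, and d = 15/510 − 3/510 = 0.02353.
- With equal arms, P = (y − x)/4 = −3.
- Q = [15 × 507/1020 + 3 × 495/1020]/2 = 4.4559.
- Variance = (0.02353 × (−3) + 4.4559)/255² = 6.744 × 10⁻⁵, so SE = 0.00821.
- Upper limit = 0.02353 + 1.96 × 0.00821 = 0.0396, below 4%: non-inferior.
- Score test: with the difference held at 4%, the restricted rates are 4.44% and 0.44%, and SE = 0.00957. Then z = (0.02353 − 0.04)/0.00957 = −1.72, short of −1.96: not shown.

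**Actual size.** Every pair of counts is enumerated with x ~ Bin(510, p + 0.04) and y ~ Bin(510, p), and the probability of declaring non-inferiority is summed.

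| Assumed Q4W rate p | Planned rule | Score (Miettinen–Nurminen) |
|---|---|---|
| 0.1% | 4.52% | 1.84% |
| 0.5% | 4.04% | 2.07% |
| 1% | 3.66% | 2.26% |
| 2% | 3.19% | 2.37% |
| 3% | 2.94% | 2.36% |
| 4% | 2.82% | 2.40% |
| 5% | 2.71% | 2.39% |
| 10% | 2.58% | 2.50% |

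**Stratification does not remove the excess.** Simulating the planned rule with three strata (2,000,000 runs per setting) gives 4.0–4.1% at a Q4W rate of 0.5%, 3.6–3.7% at 1%, 3.2% at 2%, 2.9% at 3% and 2.7% at 5%, under all three splits. Unequal stratum rates between 0.5% and 3% give 3.1–3.7%.

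**Effect on the decision.** Largest number of Q8W failures still accepted as non-inferior:

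| Q4W failures | Planned rule | Score rule |
|---|---|---|
| 3 | 15 | 13 |
| 5 | 16 | 15 |
| 8 | 18 | 17 |
| 10 | 19 | 19 |
| 15 | 23 | 22 |

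**The case against.** The strongest defence has four parts.

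- **The stated level is nominal.** The multiplier 1.96 delivers 2.5% in large samples, the Sato formula is established and correctly written, and the SAP never claims exact size. This stands as far as it goes: there is no formula error. Still, the declared level is not attained at any rate tested, and the SAP neither says so nor checks it.
- **The size of the excess rests on an assumption.** A reader might infer that the test simply runs at 3–4%. The SAP does not support that. It says only that participants are stably suppressed at entry. That makes low rates plausible but fixes no figure, and at 4–5% the excess is 0.2–0.3 points.
- **Little changes in practice.** The acceptance limit moves by 0 to 2 failures, and the 15 versus 13 example is the largest gap of the five checked. This stands: only a borderline result would be affected.
- **It is too late to switch.** Section 5.4.2 describes baseline genotypic data as arriving after the Week 48 data cut, and the display lists cite existing outputs of this study. Replacing the decision rule now would be post hoc. This also stands.

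Two further inferences go too far. The score-based subgroup interval does not show that the sponsor judged its primary method inadequate, since it is an unadjusted exact method for possibly small groups. Nor is this the only confirmatory test: Section 5.5.2 places key secondary comparisons behind it, and Section 7.1.5.1 adds a superiority test. The −10% key secondary comparison uses the same type of interval but was not assessed here.

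**Conclusion.** The point holds as a should-fix. With 510 per arm, the planned rule has a one-sided size of about 2.9–4.0% for Q4W failure rates of 0.5–3% and 2.7–2.8% at 4–5%. It exceeds 2.5% at every rate tested up to 10%, always towards declaring non-inferiority. The score rule gives 2.1–2.4% between 0.5% and 5%. Nothing else in the SAP corrects the excess.

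The figures rest on the planned 510 per arm and on assumed failure rates; the stratum splits tried made no material difference. The finding does not show that any conclusion of the trial is wrong. It shows that a result close to the 4% margin would carry weaker evidence than the stated level implies.

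**What to change.** - Keep the pre-specified CMH/Sato interval as the basis of the primary decision.
- Add to the sensitivity analyses in Section 7.1.5.1 a stratified Miettinen–Nurminen score interval, with the same strata and CMH weights. Apply it at Weeks 48, 96 and 152 and to the Per-Protocol repeats.
- Label it as added after the Week 48 data cut, and report at each time point whether the upper limit is below 4% under both intervals.
- In Section 5.5.1, describe the one-sided 2.5% as the nominal level.

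The cost is a few sentences, one standard software option and an extra line in existing tables. As a sensitivity analysis it leaves the power of the primary test unchanged.

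Had the Week 48 analysis not yet been done, the score interval should have been the primary one. Its power cost would have been small: 99.3% to 98.7% at equal 2% rates, 96.0% to 94.5% at 3%, and 90.1% to 88.2% at 4%.

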7.2. Secondary Efficacy Analyses

7.2.1. Endpoints

The key secondary efficacy endpoint is the proportion of participants with plasma HIV-1 RNA < 50 c/mL at Week 48 using the FDA Snapshot algorithm (Intent-to-Treat Exposed [ITT-E] population).

Other secondary efficacy endpoints for the study are listed below:

- Proportion of participants with plasma HIV-1 RNA < 50 c/mL at Week 24, Week 96 and Week 152 using the FDA Snapshot algorithm (ITT-E population)
- Proportion of participants with plasma HIV-1 RNA < 50 c/mL over time (including at Sub-study Week 16) using the FDA Snapshot algorithm during the Sub-study Thigh Injection phase (Sub-study ITT-E population)
- Proportion of participants with protocol-defined confirmed virologic failure (CVF) through Week 24, Week 48, Week 96 and Week 152
- Proportion of participants with protocol-defined confirmed virologic failure (CVF) through the Sub-study Thigh Injection phase

- Proportion of participants with HIV-1 RNA ≥ 50 c/mL as per FDA Snapshot algorithm at Week 24, Week 96 and Week 152
- Proportion of participants with plasma HIV-1 RNA ≥ 50 c/mL over time (including at Sub-study Week 16) using the FDA Snapshot algorithm during the Sub-study Thigh Injection phase
- Absolute values and changes from Baseline in viral load and CD4+ cell counts over time including Week 48, Week 96 and Week 152

7.2.2. Summary Measure

Difference in the proportion of participants with HIV-1 RNA < 50 c/mL at Week 24, Week 48, Week 96 and Week 152 (defined by the US FDA snapshot algorithm) between each treatment group (Q8W – Q4W).

Difference in the proportion of participants with HIV-1 RNA ≥ 50 c/mL at Week 24, Week 96 and Week 152 (defined by the US FDA snapshot algorithm) between each treatment group (Q8W – Q4W).

7.2.3. Population of Interest

The secondary efficacy analyses will be based on the Intent-to-Treat Exposed population, unless otherwise specified.

7.2.4. Strategy for Intercurrent (Post-Randomization) Events

As defined by the snapshot algorithm, participants with last available HIV-1 RNA measurement less than 50 c/mL while the participant is on treatment within the analysis visit window of interest are classified as HIV-1 RNA < 50 c/mL.

Participants without on-treatment HIV-1 RNA data for the visit of interest and who discontinue treatment for reasons not related to adverse event while having HIV-1 RNA ≥ 50 c/mL at time of discontinuation or who change study treatment not permitted per protocol before the analysis window are classified as having HIV-1 RNA ≥ 50 c/mL.

7.2.5. Statistical Analyses / Methods

Details of the planned displays are provided in [Appendix 15](#): List of Data Displays and will be based on GSK data standards and statistical principles.

Unless otherwise specified, endpoints / variables defined in Section [7.2.1](#) will be summarised using descriptive statistics, graphically presented (where appropriate) and listed.

7.2.5.1. Statistical Methodology Specification

| Key Secondary Statistical Analysis |
|---|
| Endpoint |
| 
 • Proportion of participants with plasma HIV-1 RNA < 50 c/mL at Week 48 using the FDA Snapshot algorithm (Intent-to-Treat Exposed [ITT-E] population) |

| Key Secondary Statistical Analysis |
|--|
| Snapshot Dataset |
| • As Section 7.1.5.1 and Section 15.9 |
| Model Specification |
| • As specified in Section 7.1.5.1 but with 'HIV-1 RNA <50 c/mL' replacing HIV-1 \geq 50 c/mL |

| Key Secondary Statistical Analysis | |
|--|--|
| Model Results Presentation | |
| 
Adjusted CMH estimate of the difference in the proportion of participants with HIV-1 RNA < 50 c/mL at Week 48 between each treatment group (Q8W – Q4W) and corresponding 95% confidence interval.Non-inferiority will be concluded if the lower bound of the two-sided 95% confidence interval for the CMH adjusted treatment difference (Q8W – Q4W) is greater than -10%. | |
| Subgroup Analyses | |
| 
As specified in Section 7.1.5.1 but with HIV-1 RNA < 50 c/mL replacing 'HIV-1 RNA \geq 50 c/mL'. | |
| Sensitivity and Supportive Analyses | |
| 
Per-protocol population analysis:
To assess the impact of important protocol deviations, statistical analysis will be repeated using the Per-protocol population and compared for consistency with the results from the primary ITT-E population analysis. | |

7.3. Exploratory Efficacy Analyses

Table 3 provides an overview of the planned exploratory efficacy analyses. Details of the planned displays are provided in Appendix 15: List of Data Displays and will be based on GSK data standards and statistical principles. The exploratory efficacy analyses will be based on the Intent-to-Treat Exposed population, unless otherwise specified.

Table 3 Overview of Exploratory Efficacy Analyses

| Endpoints | Absolute | | | | | | Change from Baseline | | | | | |
|---|----------------|---|---|------------------|------------------|-------------------|----------------------|---|---|---------|---|------------------|
| | Stats Analysis | | | Summary | | Individual | Stats Analysis | | | Summary | | Individual |
| | T | F | L | T | F | F | T | F | L | T | F | F |
| Proportion of participants without efficacy-related discontinuation (ERDF) or treatment-related discontinuation (TRDF) failure at Week 24/Week 48/Week 96/Week 152 | | | | | | | | | | | | |
| Kaplan-Meier estimate | | | | Y | | | | | | | | |
| Proportion of participants with plasma HIV-1 RNA ≥ 50 c/mL over time (Maintenance Phase) - Snapshot | | | | | | | | | | | | |
| by visit | | | | Y | Y ^[1] | | | | | | | |
| By visit and subgroup | | | | Y | Y ^[2] | | | | | | | |
| Proportion of participants with plasma HIV-1 RNA < 50 c/mL over time (Maintenance Phase) - Snapshot | | | | | | | | | | | | |
| by visit | | | | Y | Y ^[3] | | | | | | | |
| By visit and subgroup | | | | Y | Y ^[2] | | | | | | | |
| Proportion of participants with plasma HIV-1 RNA ≥ 200 c/mL over time (Maintenance Phase) - Snapshot | | | | | | | | | | | | |
| by visit | | | | Y | Y ^[4] | Y ^[5] | | | | | | |
| Proportion of participants with plasma HIV-1 RNA < 200 c/mL over time (Maintenance Phase) - Snapshot | | | | | | | | | | | | |
| by visit | | | | Y | Y ^[4] | Y ^[5] | | | | | | |
| Proportion of participants with plasma HIV-1 RNA ≥ 50 c/mL at Week 48/Week 96/Week 152 by delay in IP injection - Snapshot | | | | | | | | | | | | |
| by delay in IP injection ^[6] | | | | Y | | | | | | | | |
| Proportion of participants with plasma HIV-1 RNA < 2 c/mL over time (Maintenance Phase) | | | | | | | | | | | | |
| by visit | | | | Y | | | | | | | | |
| Plasma HIV-1 RNA over time | | | | | | | | | | | | |
| by visit | | | | Y ^[7] | | Y ^[8] | Y ^[9] | | | | | Y ^[9] |
| Target Detected vs Target Not Detected by visit ^[10] | | | | Y | | Y ^[11] | | | | | | |
| Confirmed Virologic Failure (CVF) | | | | | | | | | | | | |
| CVF overall | | | | Y | | | | | | | | |
| CVF by visit | | | | Y | | Y | | | | | | |

| Endpoints | Absolute | | | | | | Change from Baseline | | | | | | | |
|---|----------------|---|---|---------|---|------------|----------------------|----------------|---|---|---------|---|------------|---|
| | Stats Analysis | | | Summary | | Individual | | Stats Analysis | | | Summary | | Individual | |
| | T | F | L | T | F | F | L | T | F | L | T | F | F | L |
| Plasma HIV-1 RNA at time of suspected and confirmed virologic failure | | | | Y | | | | | | | | | | |
| CD4+ & CD8+ Cell Counts Over Time | | | | | | | | | | | | | | |
| CD4+ observed ^[12] | | | | Y | | | | | | | Y | | | |
| CD8+ observed ^[12] | | | | Y | | | | | | | Y | | | |
| CD4+/CD8+ ratio observed ^[12] | | | | Y | | | | | | | | | | |
| HIV-1 Conditions and Disease Progression | | | | | | | | | | | | | | |
| HIV Conditions including/excluding Recurrences as recorded in eCRF | | | | Y | | | | Y | | | | | | |
| HIV Disease Progressions ^[13] | | | | Y | | | | | | | | | | |

NOTES:

- T = Table, F = Figures, L = Listings, Y = Yes display generated
- Stats Analysis = Represents TFL related to any formal statistical analyses (i.e. modelling) conducted.
- Summary = Represents TF related to any summaries (i.e. descriptive statistics) of data.
- Individual = Represents FL related to any displays of individual participant's data.

1. Line plots, with 95% confidence intervals (CIs), for the proportion of participants with HIV-1 RNA ≥ 50 c/mL by treatment group at each visit. The 95% CIs will be calculated using Exact (Clopper-Pearson) confidence interval if the proportion is 0%; otherwise, they are derived using the normal approximation.
2. Plot of the unadjusted treatment difference and its 95% confidence intervals (Snapshot algorithm) overall and by subgroup at Week 48/Week 96/Week 152.
3. Line plots, with 95% confidence intervals, for the proportion of participants with HIV-1 RNA < 50 c/mL by treatment group at each visit. The 95% CIs will be calculated using Exact (Clopper-Pearson) confidence interval if the proportion is 100%; otherwise, they are derived using the normal approximation.
4. Study outcomes (i.e., HIV-1 RNA < 200 c/mL, HIV-1 RNA ≥ 200 c/mL, or reason for no data in the window) based on the snapshot algorithm at Week 48 will also be produced.
5. Line plots, with 95% confidence intervals, for the proportion of participants with HIV-1 RNA < 200 c/mL and ≥ 200 c/mL by treatment group at each visit. The 95% CIs will be calculated using Exact (Clopper-Pearson) confidence interval if the proportion is 0% or 100%; otherwise, they are derived using the normal approximation.
6. Delay in IP injection (days) is defined in Section 15.6.3.
7. Using log10 transformed values.
8. Individual plasma HIV-1 RNA only for participants who are in the category of 'viral load ≥ 50 c/mL' at Week 48 per Snapshot algorithm or who are CVF participants. The figures will display all HIV-1 RNA values collected.
9. For CVF participants, participants with viral load ≥ 50 c/mL during the Maintenance Phase, and participants with viral load ≥ 50 c/mL during the Maintenance oral lead-in period.
10. See Section 15.6.3 for definition of "Target Detected" and "Target Not Detected", and for the specification of corresponding summary table.
11. "Target Detected" and "Target Not Detected" are included in the listing for plasma HIV-1 RNA by visit.
12. Using available data without imputation for missing values.
13. See Section 15.6.3 for HIV disease progressions.

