1. INTRODUCTION

The purpose of this reporting and analysis plan (RAP) is to describe the analyses to be included in the Clinical Study Report for Protocol:

| Revision Chronology: | | |
|----------------------|-------------|--|
| 2017N326521_00 | 17-JUL-2017 | Original |
| 2017N326521_01 | 14-SEP-2017 | The primary purpose of protocol amendment # 1 is to revise the study sample size to randomize approximately 1020 participants including 510 participants per arm based on a non-inferiority margin of 4% between the CAB LA + RPV LA Q8W and Q4W arms. |
| 2017N326521_02 | 03-Jul-2018 | 
The primary reasons for amendment #2 are to:
 
 • Add the additional interim analysis of data when all subjects have completed the Week 24 visit, with the intent of expediting the submission of study results to Health Authorities; • Change the objective for assessing the preference for CAB LA + RPV LA every 8 weeks or CAB LA + RPV LA every 4 weeks LA compared to oral antiretroviral (ARV) and the preference for CAB LA+ RPV LA every 8 weeks compared to CAB LA + RPV LA every 4 weeks from an exploratory objective to a secondary objective. A change to the supporting version of the Preference questionnaire administered to participants at Week 48 (or withdrawal) is also acknowledged; • Add revisions and clarifications for the administration of health outcomes questionnaires; • Extend exclusion criterion #28 to also exclude hereditary coagulation and platelet disorders such as haemophilia or Von Willebrand Disease; • Update exclusion criterion #11 to indicate that CD4+ counts <200 cells/μL are not exclusionary; • Offer clarification that withdrawal assessments will be performed for any participant who withdraws prematurely from the Maintenance or Extension Phase. Additional guidance for participants withdrawing at Week 52 or Week 100 has been added; • Offer guidance to monitor medications that are dependent on OAT1 and OAT3 transport upon concomitant exposure with CAB; • Specify that 2-hour post-dose ECG should be performed at Day 1 and Week 48 only for participants receiving CAB LA + RPV LA as it is not required to perform 2-hour post-dose ECG for those receiving oral CAB + RPV at Day 1; |

| Revision Chronology: | | |
|----------------------|-------------|---|

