15.15.7.3. Efficacy Figures

| Efficacy Figures | | | | | |
|------------------|-----------------|------------------------|---|--|-------------|
| No. | Population | IDSL / Example Shell | Title | Programming Notes | Deliverable |
| 2.1 | Sub-study ITT-E | 207966/primary_34/F2.1 | Proportion (95% CI) of Subjects with HIV-1 RNA ≥ 50 c/mL by Visit (Thigh Injection Phase) – Snapshot Analysis | | Sub-study |
| 2.2 | Sub-study ITT-E | 207966/primary_34/F2.3 | Proportion (95% CI) of Subjects with HIV-1 RNA < 50 c/mL by Visit (Thigh Injection Phase) – Snapshot Analysis | | Sub-study |
| 2.3 | Sub-study CVF | 207966/primary_34/F2.7 | Individual Plasma HIV-1 RNA (log10 c/mL) Profiles by Visit – for CVF Subjects | Produce only when data available for the population of interest. Replace the first footnote with "First vertical reference line corresponds to the date of first thigh injection." | Sub-study |
| 2.4 | Sub-study ITT-E | 207966/primary_34/F2.8 | Individual Plasma HIV-1 RNA (log10 c/mL) Profiles by Visit for subjects Who are in the Category of 'HIV-1 RNA ≥ 50 c/mL' at Sub-study Week 16 per Snapshot Algorithm | Produce only when data available for the population of interest. Replace the first footnote with "First vertical reference line corresponds to the date of first thigh injection." | Sub-study |

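### By-visit proportion plots: using the exact interval only at 0% or 100% gives impossible limits at 1–3 failures and an upper limit that falls at the first failure

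*SAP*

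**What the plan says.** SAP section 7.3, Table 3, plans line plots by treatment arm and visit of the Snapshot proportions, each with a 95% interval. The notes choose the interval from the observed value:

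- Note 1 (≥50 c/mL): "The 95% CIs will be calculated using Exact (Clopper-Pearson) confidence interval if the proportion is 0%; otherwise, they are derived using the normal approximation".
- Note 3 (<50 c/mL): "Exact (Clopper-Pearson) confidence interval if the proportion is 100%; otherwise, they are derived using the normal approximation".
- Note 5 (<200 and ≥200 c/mL): "Exact (Clopper-Pearson) confidence interval if the proportion is 0% or 100%; otherwise, they are derived using the normal approximation".

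The notes give no truncation at 0% or 100% and no minimum event count for the normal approximation.

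Section 15.15.5.3 lists the outputs. Figures 2.1 (≥50 c/mL) and 2.3 (<50 c/mL) are headline, Week 48 and Week 96 deliverables. Figures 2.5 and 2.6 (200 c/mL) are Week 48 and Week 96 only. All four recur for Week 152 in section 15.15.6.3. Section 15.15.7.3 lists two sub-study figures of the same kind, "by Visit (Thigh Injection Phase"), built on main-study shells and without an interval rule of their own.

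**The concern.** Virologic failure is expected to be uncommon in a suppressed population, so the ≥50 and ≥200 c/mL proportions should lie near 0%. The normal approximation is weakest there. By making an exception at exactly 0% or 100%, the plan acknowledges this, but it leaves the neighbouring counts unprotected. The interval changes method between zero failures and one, and the two methods do not join up.

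What is at stake is how the figures read. An error bar that extends below zero is visibly wrong. An upper end that drops when a failure is observed makes an arm with one failure look better bounded than an arm with none. For a failure-rate plot, an upper limit that is too low is the unhelpful direction of error.

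**Working it through.** The SAP states no limits for these plots and no assumed failure rate, so there is no figure of its own to reproduce. The rule was applied as written.

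**Inputs.** 510 per arm (section 1: "randomize approximately 1020 participants including 510 participants per arm"); about 41 per arm in the sub-study (section 2.3); two-sided 95%, z = 1.96.

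**Formulas.** With x failures among n and p = x/n:
- x = 0, Clopper-Pearson: upper limit 1 − 0.025^(1/n).
- 0 < x < n, normal approximation: p ± 1.96·√(p(1−p)/n).
- Comparator at every x: Clopper-Pearson from beta quantiles.

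**Worked case, n = 510.**
- x = 0: 1 − 0.025^(1/510) = 0.72%.
- x = 1: p = 0.196%, standard error 0.1959%, half-width 0.384%, so −0.19% to 0.58%.

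| n | x | Rule as written | Clopper-Pearson |
|---|---|---|---|
| 510 | 0 | 0 to 0.72% | 0 to 0.72% |
| 510 | 1 | −0.19% to 0.58% | 0.005% to 1.09% |
| 510 | 2 | −0.15% to 0.93% | 0.05% to 1.41% |
| 510 | 3 | −0.08% to 1.25% | 0.12% to 1.71% |
| 510 | 4 | 0.02% to 1.55% | 0.21% to 2.00% |
| 41 | 0 | 0 to 8.60% | 0 to 8.60% |
| 41 | 1 | −2.28% to 7.16% | 0.06% to 12.86% |
| 41 | 2 | −1.72% to 11.47% | 0.60% to 16.53% |
| 41 | 3 | −0.65% to 15.29% | 1.54% to 19.92% |

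**Why this is not particular to these sizes.** The normal lower limit is negative when x < 1.96²·(1−p), that is x < 3.84·(1−p), so at 1, 2 and 3 failures for both sizes. For large n the upper limit is about 3.69/n at x = 0 (−ln 0.025 = 3.69) but about (1 + 1.96)/n = 2.96/n at x = 1. The fall occurred at every n checked from 7 to 1999.

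**Mirror at 100%, n = 510.** With no non-responders the lower limit is 99.28%. With one it rises to 99.42%, and the upper limit becomes 100.19%.

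**Coverage at n = 510**, by summing binomial probabilities over the counts whose interval contains the assumed true rate:

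| True rate (assumed) | Rule | Clopper-Pearson | P(1–3 failures) |
|---|---|---|---|
| 0.1% | >99.9% | 98.5% | 40% |
| 0.5% | 99.9% | 98.5% | 67% |
| 1% | 87.9% | 97.9% | 24% |
| 2% | 93.4% | 95.9% | 0.8% |
| 3% | 92.9% | 96.4% | ~0 |
| 4% | 93.2% | 95.9% | ~0 |

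Because counts are discrete, coverage jumps between neighbouring rates. At a true 1% the upper limit lies below the truth 11.5% of the time, against 0.6% for the exact interval and a nominal 2.5%. At 2% to 5% it does so about 4.6–5.8% of the time.

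**Coverage at n = 41.** The rule covers at least 99% for true rates from 0.1% up to about 7%. The chance of 1–3 failures is 34% at a true 1% and 73% at 4%.

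**The case against.** The strongest reply is that nothing is decided on these intervals. Table 3 classes the figures as summaries, not statistical analyses. The proportions are also tabulated by visit (section 15.15.5.2, Tables 2.13, 2.15, 2.17 and 2.18). Non-inferiority rests on the stratified CMH difference with the Sato variance, and subgroup differences use an unconditional exact method (both in section 7.1.5.1). All of that stands, and it limits the point to presentation and descriptive precision.

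Some stronger readings are tempting but not supported:

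- **That the upper limit is generally about half what it should be.** At n = 510 the ratio of planned to exact upper limit is 0.53 with one failure, but 0.66 with two, 0.78 with four, 0.88 with ten and 0.95 with 25. Negative limits need 1–3 failures.
- **That all these plots are headline outputs.** Only the two 50 c/mL figures are.
- **That the sub-study is where the intervals are least reliable.** The notes belong to main-study rows, and the SAP does not say that the sub-study figures follow them; this is inferred from the reused shells. If they do, overall coverage at 41 per arm is above nominal at realistic rates. The fault there is impossible limits and the falling upper limit.
- **That the <50 and <200 c/mL plots are equally exposed.** Under Snapshot (sections 15.6.3 and 15.7.2.2), participants without data in the window cannot count as suppressed. An arm with only 1–3 non-responders of any kind is therefore less likely.

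**Conclusion.** The point holds for notes 1, 3 and 5. Followed as written, the rule gives a negative lower limit at 1–3 failures, or one above 100% in the mirror case, and an upper limit that falls from 0.72% to 0.58% at the first failure with 510 per arm. These results follow from the rule and need no assumed failure rate.

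The coverage statement does need one, and the SAP gives none. At 510 per arm coverage is above 99% at a true rate of 0.5% or less, 87.9% at 1%, and generally about 92–94% between 1.5% and 5%, with misses mainly on the upper side. If the sub-study figures inherit the rule, the upper limit there falls from 8.6% to 7.2% at the first failure.

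The consequence is confined to descriptive by-visit figures. The primary analysis and the non-inferiority conclusion do not change. It is still worth correcting, because the error would be visible in two headline figures and is easy to remove.

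**What to change.** In notes 1, 3 and 5, use Clopper-Pearson (or Wilson) for every arm, visit and count, and delete the normal-approximation branch. In section 15.15.7.3, state the same rule for sub-study Figures 2.1 and 2.2, so that nothing depends on what the shells contain. Both intervals stay within 0–100%, and their upper limits rise with each failure.

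The cost is one interval option in the plotting code. No new data are needed and no decision rule changes. Intervals become noticeably wider at very low counts (one failure in 41: upper limit 12.9% instead of 7.2%) and only slightly wider from about ten failures at 510 per arm.
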